- c) **Baseline assessment:** Following the pre-screen, participants who are interested and eligible will be met at the clinic most convenient for them. The endocrinology division at CNH sees patients across 6 different outpatient clinics across Maryland, Virginia, and DC. Baseline assessments will be done via telehealth for maximum flexibility for participants or can be done in person to coincide with a quarterly endocrinology healthcare visit. At this telehealth visit, they will complete a virtual informed consent process, complete baseline questionnaires, and participate in an orientation visit, which we have found in previous studies results in strong retention and participation rates. They will receive a \$50 ClinCard for completion of this assessment and study-specific retention items (e.g., study logo water bottle).
- d) **Group participation:** A computerized randomization sequence will be created by the data manager in randomly permuted blocks. After completion of baseline assessments, allocation will be performed by the study coordinator using REDCap, which conceals the sequence. Teens will be randomized to BREATHE-T1D telehealth or HealthEd-T1D. As shown in **Table 1**, we will aim for $n=5$ youth/group and interventions will be run in parallel. If scheduling is difficult, we will recruit up to 12 for each of the first two cohorts and allow for two groups of 3 per intervention condition in order not to delay interested candidates and have enough per group. We will still maintain an overall n of 40, adjusting the numbers in the final cohort based on what we have in cohorts 1 and 2. Based upon our base BREATHE and HealthEd manuals, we anticipate that group duration will be ~6 consecutive weeks, 1-hour/week during non-school hours, with potential for duration/frequency modifications based on the adaptation phase.

Table 1. Estimated timeline for pilot and feasibility RCT of $N=40$ adolescents with T1D

Quarter 1	Quarter 2	Quarter 3	Quarter 4
Recruitment Cohort 1 $n=10-12$	Recruitment Cohort 2 $n=10-12$	Recruitment Cohort 3 $n=16-20$	
Baseline assessment Cohort 1	Baseline assessment Cohort 2	Baseline assessment Cohort 3	
Cohort 1 BREATHE-T1D telehealth $n=5-6$ HealthEd $n=5-6$	Cohort 2 BREATHE-T1D telehealth $n=5-6$ HealthEd $n=5-6$	Cohort 3 BREATHE-T1D telehealth $n=8-10$ HealthEd $n=8-10$	

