Sample size justification. Based upon our past experience⁷⁶ and recommended guidelines,⁷⁷ a total sample size of $N=10$ total stakeholders is anticipated to achieve informational redundancy.

Aim 2:

Statistical design/analytic plan. $N=40$ adolescents with T1D will be recruited for a pilot RCT of BREATHE-T1D delivered via telehealth, and HealthEd-T1D delivered via telehealth. The following table provides an overview of measures and methods of assessment for Aim 2:

Construct	Measure	Interval	Expected Outcome
Recruitment Feasibility/ Acceptability	# screened per month # enrolled per month # weeks to form cohort 3 group % eligible who enroll	Study initiation through completion of recruitment by CONSORT guidelines	30 screened per month 5 enrolled per month 12 weeks to form cohort 3 groups ≥80% eligible enroll after screen

Intervention Feasibility	% sessions attended by condition recorded by intervention facilitator	Weekly/intervention phase	≥80% attend ≥80% of BREATHE-T1D telehealth ≥80% attend ≥65% of HealthEd-T1D
Intervention Acceptability	Teen survey satisfaction ratings	Weekly/intervention phase	≥80% liking/credibility/relevance/utility ratings ≥4 (1=not at all to 5=extremely)
	Teen qualitative interview	Post-intervention follow-up	Themes indicative of liking/credibility/relevance/utility
Intervention Fidelity	[name]/[name] structured ratings of BREATHE-T1D and HealthEd-T1D adherence and competence	Weekly/intervention phase	≥8 scores on adherence and competence ratings (1=poor to 10=exceptional) for all 3 intervention conditions
Retention Feasibility/Acceptability	% complete post-treatment follow-up	Post-intervention follow-up	≥80% complete post-treatment follow-up
Assessment Feasibility	% assessments with missing vs. complete data	Baseline; post-intervention follow-up	<5% missing data for assessments administered to participants
Disposition al Mindfulness	Teen report on Mindful Attention Awareness Scale; Five-Factor Mindfulness Questionnaire	Baseline; post-intervention follow-up	<5% missing data for assessments administered to participants
			<10% will display worsening across conditions
Negative Affectivity	Teen report on PROMIS short forms Depression/ Anxiety subscales	Baseline; post-intervention follow-up	
Maladaptive Eating Behavior	Diabetes Eating Problems Survey – Revised	Baseline; post-intervention follow-up	

Negative Urgency	Teen report on UPPS-P – Negative Urgency Subscale	Baseline; post-intervention follow-up	

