Treatment Adherence	Self-Care Inventory	Baseline; post-intervention follow-up	
Glycemic Control	Hemoglobin A1c derived from the patient electronic medical record	Baseline; post-intervention follow-up	<10% will display increased A1c across conditions
Diabetes Distress	Teen report on Problem Areas in Diabetes-Teen	Baseline; post-intervention follow-up	

g) **Feasibility:** The primary focus of the feasibility assessment will be to demonstrate that a recruitment, participation, and retention can meet pre-defined targets. To evaluate feasibility, a CONSORT table and descriptive statistics regarding recruitment, retention, data completeness, and fidelity will be generated by intervention group. Feasibility will be determined overall by meeting recruitment targets and rates of agreement to participate in the study. Retention, participation, and fidelity by group will be examined for meeting feasibility criteria (>80% retention, >80% sessions attended, >80% of homework completed, 80% fidelity of intervention delivery). Feasibility indicators also will be evaluated for differences between group conditions in order to determine if one program is more feasible. For participants lost to attrition in each cohort, baseline characteristics and research coordinator feedback will be evaluated to determine how recruitment rates may be improved.

[figure not shown]
h) **Acceptability:** To evaluate acceptability quantitatively, descriptive data will be generated of post-intervention satisfaction surveys overall and by group condition. Acceptability will be determined by a high level of satisfaction with participation, perceived utility of the intervention content, and perceived benefit from participation (>80% reporting that they were satisfied and perceived utility and benefit). Acceptability indicators will also be evaluated for differences between group conditions in order to determine if one is more acceptable.

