Qualitative acceptability strand. At post-intervention, all adolescents will complete an open-ended, structured interview to query about their subjective experiences of the intervention content, relationships with facilitators/other group members, home practice completion, and enablers and barriers of making changes in coping with negation emotions, eating behaviors, and T1D treatment adherence. After coding $n=3$ BREATHE-T1D, telehealth interviews, and $n=3$ HealthEd-T1D interviews, [name] will develop a coding manual to be used by 2 trained coders, who have expertise in qualitative analysis, to code the remainder of the following qualitative post-intervention adolescent interviews. [name] will oversee coding through regular audits. To assure rich and meaningful information, we will make iterative adjustments to interview guides as needed and maintain regular communication and systematic

discussion among interviewers, data analysts, the qualitative expert ([name]), and experts in adolescents with T1D and behavioral interventions ([name] & [name]), eating ([name] & [name]) and BREATHE ([name]).

Based on the feedback received in cohorts 1 and 2, additional modifications will be made to BREATHE-T1D and HealthEd-T1D as indicated for cohorts 2 and 3. Specifically, to carry out these additional, iterative adaptations to the interventions, after each set of $n=5$ interviews, qualitative findings will be reviewed by the team to determine if there are needed, minor adjustments or tweaks to the BREATHE and/or HealthEd modules for the subsequent cohort(s).

Figure depicting qualitative strand of the study to be carried out in Aims 1 and 2:

- i) **Measurement:** Descriptive statistics using the measurements of hypothesized outcome and mechanism indicators will be used to look at variability in responses for each measure for utility of use in future trials (e.g., is there sufficient variability across participants to make it a worthwhile indicator of the proposed construct, do the measures correlate with one another in expected directions). Our primary pilot (and subsequent full-scale trial) assessments of improvement in measures will be a set of planned contrast comparisons using independent samples group t-tests with further validation using the non-parametric Wilcoxon rank sum test. These are:

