 - i) Comparison of the $n=20$ active treatment participants in BREATHE-T1D telehealth delivery to the $n=20$ HealthEd-T1D control arm participants on measures of feasibility (e.g., recruitment, dropout, data missingness, fidelity) and acceptability (e.g., satisfaction ratings) to determine if there are differences in feasibility or acceptability between BREATHE-T1D versus HealthEd-T1D.

Sample size justification. For studies that can be considered both feasibility and pilot studies we approached sample size assessment for both. There are a range of thoughts on sample sizes needed to assess feasibility.⁷⁸ Julious et al.⁷⁹ recommend $n=12$ per group as a rule of thumb and justify this recommendation based upon rationale about feasibility and precision about the mean and variance. A paper provided by the United Kingdom National Institute of Health⁸⁰ recommends a total pilot sample size between $N=30$ and $N=50$. We also assessed the 80% completion rule (which is used for several of our feasibility outcomes). If we assume a chance response of 50% program completion, with a sample size of 15 (at alpha = 0.05 and 80% power), we can detect a difference of 80% completion or more. Therefore, we believe the proposed study will be powered to assess feasibility overall and by group condition.

Concerning the sample size assessment for pilot studies, we reference Cocks and Torgerson⁸¹ who recommend using a total sample size of $N=45$ or more to detect a significant effect size of 0.25 or greater between 2 group conditions planned in the larger trial following the pilot study or to use a total sample size of $N=30$ to detect a significant effect size of 0.31 or greater between 2 group arms in the larger trial following the pilot study. Based upon our review of similar studies assessing glycemic control⁸² and mindfulness-based intervention measures,³⁴ we believe these effects size are reasonable for our 3 planned 2-group comparisons regarding our primary aims of evaluating feasibility and acceptability.

E. Study Population:

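### The planned 20 vs 20 t-test/Wilcoxon contrast lists recruitment, which has no arm value, and fidelity, which is rated per session, and ignores therapy groups for outcomes measured after groups start

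*Combined protocol and SAP*

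**What the plan says.** Section D, i) Measurement, sets out "a set of planned contrast comparisons using independent samples group t-tests with further validation using the non-parametric Wilcoxon rank sum test". The single contrast listed compares the 20 participants of one arm with the 20 of the other "on measures of feasibility (e.g., recruitment, dropout, data missingness, fidelity) and acceptability (e.g., satisfaction ratings"). Its stated purpose is "to determine if there are differences in feasibility or acceptability between BREATHE-T1D versus HealthEd-T1D".

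Section D.3 d) Group participation fixes the order of events: "After completion of baseline assessments, allocation will be performed by the study coordinator using REDCap". The same section aims for 5 teenagers per group, with the two arms run in parallel. If scheduling is difficult, it allows two groups of 3 per condition in each of the first two cohorts. It expects about 6 weekly sessions. All sessions are recorded and reviewed weekly on structured rating scales for fidelity.

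The Aim 2 table defines the recruitment measures as numbers "screened per month # enrolled per month # weeks to form cohort 3 group % eligible who enroll", counted from study start to the end of recruitment.

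Section D, g) Feasibility, points two ways on recruitment. It says "descriptive statistics regarding recruitment, retention, data completeness, and fidelity will be generated by intervention group", and then "Feasibility will be determined overall by meeting recruitment targets and rates of agreement to participate in the study". It adds: "Feasibility indicators also will be evaluated for differences between group conditions in order to determine if one program is more feasible".

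**The concern.** A participant-level two-sample test needs one value per participant, an arm to which that value belongs, and independence between participants. The listed measures fail these conditions in three different ways.

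- **Recruitment** has no arm.
- **Fidelity** belongs to a session and its facilitator, not to a teenager.
- **Outcomes after groups start** have an arm and a participant, but teenagers in one therapy group share sessions, facilitator and one another. The plan takes group process seriously enough to have cohesion rated by two independent raters, yet nothing in the analysis or sample-size text allows for therapy group. The Wilcoxon test offered as validation makes the same independence assumption, so it cannot reveal the problem.

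At stake is the answer to whether one program is more feasible or acceptable than the other, which may inform the Phase 4 refinements. Section i) also describes these contrasts as the approach for the later full-scale trial, so the wording may carry forward.

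**Working it through.** **The plan's own figure.** No sample size or power is derived for this contrast. The one calculation with full inputs (Sample size justification, n = 15) concerns a single completion rate of 80% against 50%. With one-sided alpha 0.05 and 80% power, n = [(1.645 × 0.5 + 0.842 × 0.4) / 0.3]² = 14.9, so 15 is reproduced. It is a one-sample figure and does not bear on the arm contrast.

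**Recruitment.** Screening, enrolment and the percentage of eligible teenagers who enroll are all settled before allocation. No participant has a score on any of them. Weeks to form the cohort 3 groups would give at most one value per arm even if logged separately. No contrast can be computed.

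**Fidelity.** At 5 per group there are 20 / 5 = 4 groups per arm, and 4 × 6 = 24 session ratings. With groups of 3, 3, 3, 3, 4, 4 there are 6 × 6 = 36. (The two groups of 4 in cohort 3 are an assumption, since the documents do not state that split.) The ratings are nested in 4 to 6 groups, and section i) does not say how they would enter a 20 vs 20 test.

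**Outcomes after groups start.** Assumptions: normal outcome with total variance 1, no true arm difference, ICC 0.05/0.10/0.20, and a 5% two-sided level (critical value 2.024 on 38 df).

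With 4 groups of 5 and all between-group variance specific to the therapy group:

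- Design effect DE = 1 + (5 − 1) × ICC = 1.20/1.40/1.80.
- Expected sample variance within an arm = (1 − DE/20) × 20/19 = 0.990/0.979/0.958.
- True over estimated variance of the difference = 1.213/1.430/1.879.
- Effective critical value = 2.024 / √ratio = 1.838/1.693/1.477.
- Two-sided tail area on 38 df = 7.4/9.9/14.8%.

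Simulation agrees. Rejection rates (simulated, normal outcome) are:

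| Groups per arm | Between-group variance shared by cohort across arms | ICC 0.05 | 0.10 | 0.20 |
|---|---|---|---|---|
| 5, 5, 5, 5 | none | 7.4% | 9.9% | 14.9% |
| 5, 5, 5, 5 | half | 6.0% | 7.1% | 9.4% |
| 5, 5, 5, 5 | all | 4.6% | 4.3% | 3.7% |
| 3, 3, 3, 3, 4, 4 | none | 6.4% | 7.9% | 11.0% |
| 5, 5, 10 | none | 9.0% | 12.9% | 20.5% |

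The last row assumes that cohort 3 runs as one group of 10 per arm, contrary to the aim of 5 per group. There the mean group size weighted by members is (25 + 25 + 100)/20 = 7.5, so DE = 1 + 6.5 × ICC = 1.325/1.65/2.30. The Wilcoxon test behaves like the t-test: 7.2/9.5/14.1% in the first layout with no shared variance. At ICC 0.01 that layout gives 5.5% for the t-test.

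**Binary outcomes.** With 4 groups of 5, no shared variance and ICC from 0 to 0.20 on a latent scale, the t-test rejects about 1 to 3% at a 5% event rate, about 4 to 7% at 10%, and about 5 to 10% at 20%. The plan's targets are under 5% missing data and at least 80% retention, so missingness near its target falls in the conservative range and dropout near its target does not.

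**The case against.** The strongest reply is that little depends on this test. Feasibility is judged against descriptive targets, recruitment is judged overall, and no efficacy analysis is planned. The plan attaches no decision rule to the contrast and sets no significance level for it; the 0.05 in the sample-size text belongs to the completion-rate calculation. Changes between cohorts are driven by interviews. Recruitment and fidelity appear in a list of examples, and fidelity is already to be described by group. All of this stands. It limits the consequence, but does not make the contrast computable for recruitment or give fidelity a unit.

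The size and even the direction of the clustering effect are assumed. That also stands. A reader might take 15% as a ceiling; it is not, since one group of 10 in cohort 3 gives about 21% at ICC 0.20. A reader might equally infer that every listed test is too liberal. The documents do not support that either: variance shared by cohort across the parallel arms makes the test slightly conservative, as does a rare binary outcome, and missingness at baseline precedes allocation and is untouched.

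A group-level analysis with a cohort term is not a complete cure. Content may be changed between cohorts separately for each program, which can create arm-by-cohort effects. If half or all of the ICC is of that kind, such an analysis rejects about 6 to 14% at ICC 0.05 to 0.20.

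**Conclusion.** The point holds within limits. As written, one listed comparison cannot be computed, one has no valid unit, and the error rate can be wrong for outcomes that arise in therapy groups. The first two need no assumption beyond the text. The third rests on an assumed ICC and layout. For a roughly normal outcome at a 5% level, with ICC 0.05/0.10/0.20, rejection is about 7/10/15% with 4 groups of 5 and group-specific variance, about 6/7/9% if half is shared by cohort, slightly under 5% if all is shared, and about 9/13/21% with a group of 10.

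Two stronger readings should be resisted. The plan does not state that 20 fidelity values per arm would be tested; it leaves the unit undefined. Nor is the feasibility verdict undermined: the descriptive targets remain usable, and only the between-arm determination is affected. The change should be made, since the plan commits to that determination and the repair is cheap.

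**What to change.** - **Section i), planned contrast:** remove recruitment from the arm comparison.
- **Section g):** report screening, enrolment and the percentage of eligible teenagers who enroll overall. Keep reporting by intervention group for counts after allocation.
- **Fidelity:** summarise by session and therapy group, descriptively by arm.
- **Attendance, dropout, follow-up missingness and satisfaction:** replace the t-test/Wilcoxon verdict with description by arm and by therapy group, building on the descriptive reporting already planned in g) and h), and with no significance test.
- **If intervals are wanted** for roughly continuous outcomes such as attendance or satisfaction scores: base them on therapy-group means with cohort as a factor. State that they are wide, do not suit rare binary outcomes, and do not cover arm-by-cohort effects from changing content between cohorts. Residual df = groups in both arms − 4 (intercept, arm, two cohort terms): 6 − 4 = 2, 8 − 4 = 4 or 12 − 4 = 8 for layouts 5, 5, 10; 5, 5, 5, 5; and 3, 3, 3, 3, 4, 4.

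**Cost.** Analysis wording and a therapy-group identifier in the analysis file; no new data. The description-only option gives up a formal test of arm difference. If intervals are used, then relative to the individual-level t interval they are about 1.30 times as wide at ICC 0 and 1.43/1.55/1.78 times at ICC 0.05/0.10/0.20 with 4 groups of 5 and no shared variance. With groups of 3 to 4 the figures are 1.12 and 1.19/1.25/1.37 times. With one group of 10 per arm in cohort 3 the interval is about 2.0 to 2.9 times as wide.

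### The power statement in the sample size justification is about excluding 50% completion; it does not support calling the study powered for its 80% feasibility criteria, and its n=15 figure rests on an unnamed approximation

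*Combined protocol and SAP*

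**What the plan says.** The sample size justification under Aim 2 (section D) introduces the calculation with "We also assessed the 80% completion rule (which is used for several of our feasibility outcomes". It takes 50% program completion as a chance response and states that "with a sample size of 15 (at alpha = 0.05 and 80% power), we can detect a difference of 80% completion or more". From this it infers that "we believe the proposed study will be powered to assess feasibility overall and by group condition".

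The criteria themselves stand elsewhere in Aim 2. Item g) Feasibility says: "The primary focus of the feasibility assessment will be to demonstrate that a recruitment, participation, and retention can meet pre-defined targets". It continues: "Retention, participation, and fidelity by group will be examined for meeting feasibility criteria (>80% retention, >80% sessions attended", followed by criteria at 80% for homework and fidelity. The Aim 2 table of expected outcomes gives the retention target as "≥80% complete post-treatment follow-up".

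The justification then cites two options from a published pilot-trial rule, N=45 for an effect size of 0.25 and N=30 for 0.31, each tied to the larger trial after the pilot. It closes: "we believe these effects size are reasonable for our 3 planned 2-group comparisons regarding our primary aims of evaluating feasibility and acceptability". The fidelity row of the Aim 2 table sets its target "for all 3 intervention conditions". The trial has two arms of 20, and item i) Measurement lists one comparison.

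**The concern.** Two things look wrong in the power statement. First, the figure cannot be checked without guessing the method, and n=15 is small enough for large-sample formulas and exact binomial probabilities to disagree noticeably. Second, and more important, the calculation tests completion against 50%, while no feasibility criterion in the plan is set at 50%. Showing that completion exceeds 50% is a different question from showing that an 80% target is met.

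The plan makes meeting its targets the primary focus, and the results are meant to shape a later efficacy trial. A reader who takes the word powered at face value could treat an observed 80% as established when the data are compatible with a much lower rate. Separately, the two versions of the retention criterion would let the same result be reported as met or not met.

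**Working it through.** **Inputs.** From the sample size justification: null rate 50%, alternative 80% (the text speaks of a difference of 80%; I read it as a completion rate of 80%), n=15, alpha 0.05, power 80%. From sections D and E: 20 per arm, 40 in total. Sidedness and test are not stated, so both sides were tried. Participants are treated as independent.

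**1. Reproducing n=15.** One-sample normal formula, one-sided, no continuity correction:

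n = [(1.645 × 0.5 + 0.8416 × 0.4) / 0.3]² = (1.1591 / 0.3)² = 14.93, rounded up to 15.

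The one-sided arcsine formula also gives 14.93. The two-sided versions give 19.26 (normal) and 18.95 (arcsine), and a two-sided formula using only the variance at 80% gives 13.95. The stated figure is therefore a one-sided large-sample result, not a slip.

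**2. What n=15 gives exactly.** The normal cutoff is 7.5 + 1.645 × √(15 × 0.25) = 10.69, that is 11/15.

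- Reject at 11 or more: P(X ≥ 11 | 0.5) = 1941/32768 = 0.059, above alpha; power P(X ≥ 11 | 0.8) = 83.6%.
- Reject at 12 or more: P(X ≥ 12 | 0.5) = 576/32768 = 0.018; power P(X ≥ 12 | 0.8) = 64.8%.

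Twice 0.0176 is 0.035, so 12/15 is the exact cutoff one- or two-sided.

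**3. The planned sizes, against 50%.** At n=20, P(X ≥ 15 | 0.5) = 21700/1048576 = 0.0207, or 0.041 doubled. P(X ≥ 14 | 0.5) = 60460/1048576 = 0.058, which is too large. The cutoff is 15/20 either way.

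| n | Exact power, one-sided | Exact power, two-sided |
|---|---|---|
| 15 | 64.8% | 64.8% |
| 16 | 79.8% | 59.8% |
| 19 | 83.7% | 67.3% |
| 20 | 80.4% | 80.4% |
| 40 | 99.2% | 98.1% |

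**4. The 80% criteria, for a participant-level proportion such as retention.**

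- 15/20 (75%) rejects 50% but is below 80%. Its exact 95% confidence interval is 51% to 91%.
- 16/20 (80%) has an exact interval of 56% to 94%; 32/40 has 64% to 91%.
- If true retention is 80%, an arm of 20 shows at least 80% with probability 63%, and above 80% with probability 41%.
- If true retention is 70%, an arm of 20 still shows at least 80% with probability 24%.

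**5. Retention wording.** At least 80% means 16/20 or more; above 80% means 17/20 or more. A result of 16/20 meets the table and fails item g).

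**6. Effect sizes and counts.** 30 ≤ 40 < 45, so N=40 satisfies the N=30 (0.31) option and not the N=45 (0.25) option. Two arms give one two-group comparison, not three.

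**The case against.** The strongest reply is that little hangs on n=15. The trial does not use that size, and at 20 per arm the exact test against 50% reaches 80%. The 64.8% partly reflects the discreteness of the exact test, whose real type I error is 0.018. A one-sided mid-p test would reject at 11/15 (0.0176 + 0.0417/2 = 0.038) with 83.6% power. All of that stands. What remains is that the method is unnamed, and that the cutoff giving power above 80% carries a true type I error of 0.059 against a stated 0.05.

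A reader might infer that the planned arms are underpowered against 50%, or that any loss from 20 per arm removes the power. The documents do not support either. Below 20 the answer depends on a sidedness that the plan does not state: one-sided power is 79.8% at n=16 and 83.7% at n=19, while two-sided power is 59.8% and 67.3%.

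It can also be said that the feasibility criteria are descriptive, and that the sample size also rests on two published rules of thumb (12 per group; 30 to 50 in total). That is correct. One might be tempted to require a confidence limit above 80%, but the plan sets no such standard and a pilot need not. The objection here is narrower: the plan itself presents the calculation as an assessment of its 80% rule and draws the word powered from it.

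Finally, the effect sizes 0.25 and 0.31 are tied twice to the larger trial, so the plan does not plainly claim them for the pilot. Only the closing sentence, which attaches them to feasibility and acceptability comparisons, blurs this.

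**Conclusion.** The point holds as a minor one, with three parts.

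- **Power figure.** The 80% at n=15 is an unnamed one-sided approximation; exact power is 64.8%. The planned 20 per arm has 80.4% exact power against 50%, so the design is adequate for that question.
- **Inference.** This is the substantive error. Excluding 50% does not show that the 80% criteria are met. With 20 per arm, an observed 80% leaves a range of 56% to 94%, and a true rate of 70% still yields an observed 80% or more about one time in four.
- **Inconsistent text.** The retention threshold differs at exactly 80%, and references to three comparisons and three conditions do not fit a two-arm trial with one listed comparison.

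The figures assume independent participants, all counted in the denominator. Delivery is in small groups, so clustering could widen the intervals. They apply to participant-level proportions such as retention; percentages of sessions attended and fidelity ratings are not simple binomial counts.

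**What to change.** 1. Replace the n=15 sentence with the planned size: with 20 per arm, an exact binomial test of 50% completion at alpha 0.05 (reject at 15/20 or more) has 80.4% power if true completion is 80%. Name the test and sidedness. Note that power with fewer participants depends on sidedness (n=19: 84% one-sided, 67% two-sided; n=16: 80% and 60%), and that participants are treated as independent.
2. Say that the study is powered to exclude 50% completion, not to show that the 80% criteria are met. Report participant-level proportions such as retention with exact 95% confidence intervals beside the planned descriptive percentages.
3. Use one retention criterion in the Aim 2 table and in item g) Feasibility.
4. Reconcile the references to three comparisons and three conditions with the two-arm design. State that 0.25 and 0.31 concern the larger trial, and that N=40 meets the N=30 option but not the N=45 option.

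The cost is text edits and a few intervals in the report. The exact test in item 1 describes the basis for the sample size; if it is not to be run as an analysis, one clause should say so. No participants are added.

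### The sample-size section offers effect sizes meant for a later trial (0.25 and 0.31) as support for this pilot's own between-arm comparisons, which 20 v 20 cannot resolve at that size

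*Combined protocol and SAP*

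**What the plan says.** All of this is in the section on data analysis, statistical design and power, under Aim 2.

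- **Sample size justification, second paragraph.** A total of 45 is recommended "to detect a significant effect size of 0.25 or greater between 2 group conditions planned in the larger trial following the pilot study", or a total of 30 "to detect a significant effect size of 0.31 or greater between 2 group arms in the larger trial following the pilot study". The closing sentence turns to the present study: "we believe these effects size are reasonable for our 3 planned 2-group comparisons regarding our primary aims of evaluating feasibility and acceptability".
- **Item i) Measurement.** The analysis is a set of "planned contrast comparisons using independent samples group t-tests with further validation using the non-parametric Wilcoxon rank sum test". One contrast is listed: "Comparison of the $n=20$ active treatment participants in BREATHE-T1D telehealth delivery to the $n=20$ HealthEd-T1D control arm participants", on measures of feasibility and acceptability.
- **Item g) Feasibility.** "Feasibility indicators also will be evaluated for differences between group conditions in order to determine if one program is more feasible".
- **Item h) Acceptability.** "Acceptability indicators will also be evaluated for differences between group conditions in order to determine if one is more acceptable".

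The first paragraph of the justification does contain a power statement (15 participants, 50% v 80% completion, alpha 0.05, 80% power), and concludes that the study is powered for feasibility overall and by condition. That calculation concerns a single proportion within one group. No alpha, sidedness, effect-size scale or power is given for the comparison between arms.

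**The concern.** The effect sizes change owner between two consecutive sentences. They are introduced as effects in a future trial and then used to support this pilot's comparisons of feasibility and acceptability. The sources cited for their plausibility concern glycemic control and mindfulness measures, not attendance, dropout or satisfaction.

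The paragraph also does not fit the design. Two arms allow one pairwise contrast and one is listed, yet three are counted. The total of 45 attached to 0.25 exceeds the 40 to be enrolled.

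What is at stake is interpretation. Items g), h) and i) use between-arm tests to decide whether the programs differ. A reader of the sample-size section could believe that those tests are sensitive to differences of 0.25 to 0.31. They are not, and the plan does not say how a non-significant result should be read.

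**Working it through.** **Inputs.** Effects of 0.25 (N=45) and 0.31 (N=30): sample size justification. Arms of 20 and 20, two-sample t-test with Wilcoxon rank sum as validation: item i). Retention target of at least 80%: Aim 2 table, so 0.80 × 20 = 16 per arm at the lowest rate that meets it. Assumptions, because the plan is silent: the effects are standardised mean differences d, and alpha is 5%, taken two-sided and then one-sided.

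**1. Reproducing the plan's pairs.** The reference list titles the cited method a confidence interval approach. The half-width of a one-sided 80% interval for a standardised difference with two equal arms is z(0.80) × 2/√N, with z(0.80) = 0.8416.

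- N=45: 0.8416 × 2/√45 = 0.251
- N=30: 0.8416 × 2/√30 = 0.307

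Both pairs reproduce. The 80% one-sided level is inferred from this match and is not stated in the plan. As two-sided 5% t-tests the same pairs have only 13.0% power each. So they are not effects that a pilot of that size can detect.

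**2. What N=40 corresponds to.** It lies between the two quoted points. Scaling each by 1/√N gives 0.25 × √(45/40) = 0.265 and 0.31 × √(30/40) = 0.268, or about 0.27. This is an interpolation, not a figure from the cited rule.

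**3. Power of this pilot's own contrast.** The noncentrality is d × √(n/2), with 38 degrees of freedom at 20 v 20.

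- d=0.25: 0.25 × √10 = 0.79
- d=0.31: 0.31 × √10 = 0.98

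| Setting | Power, d=0.25 | Power, d=0.31 | d for 80% power |
|---|---|---|---|
| 20 v 20, two-sided 5% | 12.0% | 15.9% | 0.91 |
| 20 v 20, one-sided 5% | 19.3% | 24.8% | 0.80 |
| 16 v 16, two-sided 5% | 10.5% | 13.6% | 1.02 |

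A simulation of the Wilcoxon test at 20 v 20 (20,000 runs, normal data, two-sided 5%) gives about 12% and 15%.

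**4. Other readings at 20 v 20.** Splitting two-sided 5% over three comparisons gives 5.2% and 7.4%. Reading the effects as Cohen's f gives 34% and 48%. None comes near 80%. Reaching 80% two-sided would take about 253 per arm for d=0.25 or 165 for d=0.31.

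**5. Precision.** The 95% interval for a difference in means at 20 v 20 has a half-width of about 2.024 × √(2/20) = 0.64 SD. An observed difference near zero would therefore still be compatible with a true difference of more than half an SD either way.

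**The case against.** The best defence is that the sentence is loosely worded and makes no power claim. The paragraph twice assigns the effects to the later trial, item i) says its contrasts serve both the pilot and the full-scale trial, and the cited support concerns later-trial outcomes. The author may have meant only that such effects are plausible later, with a misplaced closing clause. It is true that no 80% power is claimed for the between-arm contrast, and a reader should not infer one. But the sentence as it stands attaches the effects to the feasibility and acceptability comparisons, and those are this pilot's aims.

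Three stronger readings are tempting, and the documents do not support them.

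- **Low power would carry a poorly attended or disliked control into the efficacy trial.** Item g) makes meeting pre-set targets the primary focus, and the targets are examined by group. HealthEd-T1D has its own attendance target, satisfaction is described by condition against a threshold, all adolescents are interviewed, and the programs can be modified between cohorts. A weak control can miss its own targets whatever the between-arm p-value.
- **The attendance targets amount to a test of 80% v 65% of adolescents.** In the Aim 2 table the share of adolescents is at least 80% in both arms, and 80% and 65% are thresholds for sessions attended. No power figure should be built on that contrast.
- **The paragraph was left over from a three-arm design.** The count of three, and the table's fidelity row, which also refers to three conditions, would fit that. The history remains an inference; only the mismatch is in the text.

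The rest of the sample-size case (12 per group, or a total of 30 to 50) is untouched.

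**Conclusion.** The point stands as a misapplied justification. The quoted pairs reproduce, so there is no arithmetic slip. Effect sizes for a later trial are offered in support of this pilot's own comparisons, the count of three does not match the one contrast listed, and 40 participants do not meet the condition of 45 attached to 0.25.

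For effects of that size the 20 v 20 contrast has 12% to 16% power two-sided, or 19% to 25% one-sided. It reaches 80% only at about 0.91 SD two-sided or 0.80 SD one-sided, and at about 1.02 SD two-sided if 16 per arm remain. These figures assume standardised mean differences and a 5% level, neither of which the plan states for this contrast; power is low under every reading tried.

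The practical consequence is limited: the between-arm tests cannot establish that the programs do not differ. The pilot's validity and its per-arm feasibility criteria are not in question. The text should be corrected.

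**What to change.** In the Aim 2 sample size justification:

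- State that 0.25 and 0.31 refer to the later trial. If a value for N=40 is wanted, give about 0.27 and label it an interpolation by 1/√N between the two quoted points.
- Replace the three planned comparisons with the one that is planned.
- State that within this pilot 20 v 20 has 80% power only for differences of about 0.9 SD (two-sided 5%).

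In items g) and h), and in item i) with its listed contrast, replace the aim of determining whether the programs differ with estimating the between-arm difference, reported with a 95% confidence interval. Keep any t-test or Wilcoxon result as supportive, and say that a non-significant difference is not taken as equality. All of these places need to change together, or the plan will contradict itself.

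The cost is wording only. The stated detectable difference becomes less favourable, and no extra participants are needed.
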